## **Methodology**

### **Participants**

NAFLD patients who attending the Gastroenterology Clinic at Hospital Universiti Sains Malaysia, a tertiary referral centre for the north-eastern Peninsular Malaysia, will be screen from August 2015 till July 2016.

During the first visit, if participants met the selection criteria, informed consent are then taken. Demographic data of participants are recorded. All participants are required to complete a two-week run-in period consisting of maintaining and self-monitoring their usual dietary and daily activities.

[figure not shown]
Participants who fulfilled the selection criteria are randomly assign to the MACR group or the control group after a 2 week run-in period. During the 2 weeks, participants are requiring to keep their body weight stable by maintaining their usual eating habits and their daily activities. Randomization is performed using a random number generator with recruitment aimed for three MACR participants for every control participant by principal investigator. Calculated sample size of 46 participants would achieve a significant difference in studied outcome between intervention and control group using a two-sided test with  $\alpha = 0.05$  and power = 0.8. Participants are blinded after assignment to interventions or control group.

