## **Procedures**

A standardized calibrated balance (Secca, ZT-120, and Hamburg, Germany) will be used to measure weight of participants in light clothing at each visit. A wall-mounted stadiometer (Secca, ZT-120, Hamburg, Germany) is used to measure height (in m), and together with weight (in Kg), body mass index (BMI) is calculated. Waist circumferences are measured with the participants standing, and with the measuring tape kept horizontal and measured at a level midway between the superior aspect of the iliac crests and the lower lateral margins of the ribs.

Blood samples - 8-10 hours of fasting blood samples are collected at 8-10 am at baseline and within 1 week post intervention for biochemical analysis. High-density lipoprotein (HDL), low-density lipoprotein (LDL), triglycerides (TG), total cholesterol, fasting blood sugar and liver enzymes (alanine aminotransferase, ALT and aspartate aminotransferase, AST) are measured.

Ultra-sonographic measurements including liver steatosis and shear wave elastography (SWE) are performed with the SuperSonic Imagine's Aixplorer® Ultrasound machine (Super Sonic Image, Aix-en Provence, France). All measurements are performed by a single sonographer ([name]) where the inter-observer agreement level with another experienced sonographer ([name]) is 85%. Hepatic steatosis is graded as normal (grade 0), mild (grade 1), moderate (grade 2) and severe (grade 3) based on visual analysis of intensity of echogenicity with an appropriate gain setting based on standardised parameter (13-14). Homogenous echotexture and echogenicity equal or slightly more than the renal cortex and spleen are characteristics of a normal liver. Liver echogenicity would be higher than the renal cortex and spleen if there was hepatic steatosis.

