Through the intercostal approach, SWE measurements are performed in the right liver lobe, at the supine position with the right arm in maximal abduction. The sonographer, assist by an ultrasonic time-motion image, located a liver portion of at least 6 cm thick, free of large vascular structures. Once the measurement area had been located, the sonographer presses the probe button to start an acquisition. Patients are asked to hold their breath for about five seconds, while the stiffness of the region of interest was measured and 10 measurements are made for each patient and the median average value of those measurements is recorded in kilopascals (kPa: metric). Based on median liver elastography values, previously published four categories could be determined for different fibrosis stage.

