## **Data management and statistical analysis**

Descriptive statistics are computed for all variables; means with standard deviations (SD) for continuous variables, median with interquartile range (IQR) for ordinal data and frequencies with percentages for categorical variables. Using Kolmogorov-Smirnov analysis, the data were normally distributed if the skewness is within the range of  $\pm 2$  time standard error (SE)

of skewness. Per-protocol (PP) and intention-to-treat (ITT) analysis are performed where comparison is made within-group (post- vs. pre-intervention for each intervention and control group) and between-group (MACR vs. control). Missing data are imputed using multiple imputation method. Independent *t*-test is used to analyse changes in weight, liver chemistry, lipid profile variables, fasting blood sugar and ultrasonographic changes of liver steatosis and fibrosis between the MACR and control group. SPSS version 22 (SPSS Inc., Chicago, United States) is used for all statistical analysis. All *P* values quoted were two-sided with  $P < 0.05$  considered as statistically significant. Sample size is 46 participants with 80% power of the study.

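### The between-arm t-test on changes uses no baseline covariate: it is valid, but under a common baseline slope clearly different from 1 it gives up precision that baseline adjustment would recover cheaply

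*Combined protocol and SAP*

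**What the plan says.** Data management and statistical analysis is the only analysis text. It states that an independent t-test "is used to analyse changes in weight, liver chemistry, lipid profile variables, fasting blood sugar and ultrasonographic changes of liver steatosis and fibrosis", comparing MACR with control. The tests are two-sided at 0.05, in both per-protocol and intention-to-treat sets. It adds that "Missing data are imputed using multiple imputation method", without describing the imputation model, and that "SPSS version 22 (SPSS Inc., Chicago, United States) is used for all statistical analysis". No regression, covariate or stratification factor appears there or elsewhere.

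The baselines exist. Under Procedures, fasting bloods "are collected at 8-10 am at baseline and within 1 week post intervention for biochemical analysis"; weight is measured at each visit. For elastography "the median average value of those measurements is recorded in kilopascals", although "previously published four categories could be determined for different fibrosis stage" as well. BMI is part of the primary objective but is missing from the t-test sentence.

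Under Participants, randomisation is by random number generator, with "recruitment aimed for three MACR participants for every control participant", and the total is 46.

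**The concern.** A change score fixes the slope of the post value on baseline at 1. If the true slope is lower, subtracting the whole baseline over-corrects any chance difference between arms at entry; if it is higher, it under-corrects. Either way, variation that the baseline could explain stays in the error term. A baseline table may reveal a chance gap, but the planned P value makes no allowance for it.

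Precision is scarce: 46 at 3:1 leaves about 12 controls. For liver enzymes a slope below 1 is plausible, because the inclusion criteria select on raised ALT or AST and some regression to the mean should follow. If no adjusted model is specified now, choosing one later could look driven by the results.

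**Working it through.** **Inputs from the documents.** N = 46, 80% power, two-sided alpha 0.05, and 3:1 allocation. 46 × 3/4 = 34.5, taken as 34:12. Effect size, SDs and pre-post correlation are not given.

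**The plan's own figure.** Without an effect size and SD, 46 can be neither reproduced nor refuted. Inverted with the exact t distribution (44 df), 80% power needs a non-centrality of 2.865. That is an effect of 2.865 × √(1/34 + 1/12) = 2.865 × 0.336 = 0.96 SD of change.

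**Precision.** Set the baseline SD to 1, the post/pre SD ratio to k and the correlation to rho. The common slope is then rho·k.

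- Variance of change: 1 + k² − 2·rho·k.
- Variance of post given baseline: k²(1 − rho²).
- Difference: (1 − rho·k)², which is zero only at slope 1.
- Estimating the slope at N = 46 multiplies the ANCOVA variance by about 1 + 1/42 = 1.024.

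With equal SDs (k = 1), the ratio of ANCOVA to change variance is (1 + rho)/2 × 1.024. ANCOVA power follows from non-centrality 2.865/√ratio on 43 df, where the t-test has 80%:

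| rho | variance ratio | non-centrality | ANCOVA power |
|---|---|---|---|
| 0.3 | 0.666 | 3.51 | 93% |
| 0.5 | 0.768 | 3.27 | 89% |
| 0.7 | 0.870 | 3.07 | 85% |
| 0.9 | 0.973 | 2.90 | 81% |
| 0.95 | 0.998 | 2.87 | 80% |

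Break-even is at rho = 2 × 42/43 − 1 = 0.953; at 0.98, ANCOVA has 79%.

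**Other SD ratios**, at rho 0.3, 0.5, 0.7 and 0.9:

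- k = 0.8: 97%, 96%, 94%, 94%.
- k = 1.25: 88%, 83%, 80%, 81%.
- k = 1.5: 84%, 81%, 79%, 88%.

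ANCOVA falls just below 80% at some slopes other than 1: 79.8% at slope 0.875 (k = 1.25, rho 0.7) and 79.1% at slope 1.05 (k = 1.5, rho 0.7). At slope exactly 1 it has 79.0%.

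**ALT and AST.** If only the upper half of a normal baseline qualifies (an assumption; baseline variance 0.363, k = 1), ANCOVA power is 86%, 83%, 82% and 80%.

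**Chance baseline gap.** The SE of the gap is 0.336 SD at 34:12, so a gap of 0.5 SD or more arises in 13.6% of randomisations. At 1:1 the SE is 0.295 SD and the figure is 9.0%. The change score leaves (slope − 1) × gap in the estimate; at slope 0.5 and a gap of 0.5 SD, that is −0.25 SD. Simulated type I error of the t-test (120,000 trials per setting, equal SDs):

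| rho | given such a gap | without it |
|---|---|---|
| 0.3 | 15.7% | 3.2% |
| 0.5 | 12.9% | 3.8% |
| 0.7 | 10.0% | 4.3% |
| 0.9 | 6.7% | 4.7% |

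These average back to the nominal level: at rho 0.3, 0.136 × 15.7% + 0.864 × 3.2% = 4.9%. Under a common slope, ANCOVA stays at 4.7–5.3% either way.

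**Imputation.** With an assumed 20% of post values missing completely at random, and arm and baseline in the imputation model, power is 84%, 79%, 74% and 69% for ANCOVA against 71%, 71%, 70% and 68% for the t-test at rho 0.3, 0.5, 0.7 and 0.9.

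**Where ANCOVA does worse.** All ANCOVA figures above assume one slope for both arms. With assumed slopes of 0.5 (MACR) and 1.0 (control) and residual SD 0.5, simulation at 34:12 gives a variance ratio of 1.16 and ANCOVA type I error of about 7% overall and 13% given a gap of 0.5 SD or more. The planned t-test has about 2% and 3%, and the unequal-variance t-test 5% overall. At slopes 0.4 and 1.0 the ratio is 1.22; a baseline-by-arm term brings it to 0.98.

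**The case against.** The strongest case against acting has four parts.

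First, the test is sound. It is unbiased and holds its level overall, and the inflation after a chance gap is offset by error below 5% otherwise. This stands: a reader might infer that the planned P values are wrong or biased, and the documents do not support that.

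Second, a reader might infer that adjustment wins at every slope other than 1, or can never cost more than a point. Neither is true. At N = 46 estimating the slope costs about 2.4% of variance, so near slope 1 the t-test is marginally ahead. With strongly different slopes at 3:1, common-slope ANCOVA can be clearly less precise and exceed 5% error. The documents give neither a common slope nor separate ones, and a diet effect that varies with baseline would produce the latter.

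Third, the size is conjectural. The largest gains come from rho 0.3; for weight and BMI, measured on a calibrated balance after a weight-stable run-in, the correlation is plausibly 0.9 or more. This also stands, and is why only a range can be given.

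Fourth, ordinary ANCOVA does not cure unequal variances. With the control residual SD 1.5 to 2 times larger, its type I error is 10–15%, against 9–15% for the planned test. That calls for a robust sensitivity analysis; it is no reason to leave the baseline out.

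Nor does the 3:1 ratio cause the weakness under a common slope: it makes chance gaps about 14% larger than 1:1 (0.336/0.295), nothing more.

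**Conclusion.** The point holds as a cheap improvement, not as a defect that invalidates the analysis. For outcomes with moderate pre-post correlation and a common slope clearly different from 1, adjustment adds roughly 5 to 13 power points to a nominal 80% (rho 0.7 down to 0.3, equal SDs, 34:12) and removes the dependence on a chance baseline gap. Under the assumed entry selection, the gain for ALT and AST is at most about 6 points. It is about nil for any outcome with a slope near 1, where up to 1 point is lost. The correlations, SD ratios and slopes are all assumptions. The documents do not settle which outcomes would benefit, or whether the arms share a slope.

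**What to change.** In Data management and statistical analysis, before between-arm results are seen, replace the t-test for continuous outcomes with wording such as:

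> For weight, BMI, ALT, AST, HDL, LDL, triglycerides, total cholesterol, fasting blood sugar and median SWE (kPa), arms are compared with a linear model of the post-intervention value on arm and the baseline value of the same outcome, fitted in each imputed dataset and pooled. The imputation model includes arm and baseline. A sensitivity analysis adds a mean-centred baseline-by-arm term, with variance-robust standard errors where available; the unequal-variance t-test on change is reported beside it.

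The arm coefficient is the same whether the response is the post value or the change, so the objective of comparing changes is kept. Naming kPa settles which elastography measure is modelled. Steatosis grade can stay on the planned test; because the plan itself uses "median with interquartile range (IQR) for ordinal data", a baseline-adjusted ordinal analysis is an optional supplement.

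The cost is SAP wording, with no new data. The downsides are one degree of freedom per outcome, up to 1 point of power if a common slope is near 1, no protection from unequal SDs in the main model, and the risk from strongly different slopes, which the sensitivity analysis is there to expose. Whether SPSS 22 offers suitable robust standard errors was not verified, so the unequal-variance t-test also serves as the fallback.

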### **Expected outcomes and benefit of the study**

This study is the first to determine that modified alternate day calorie restriction (MACR) is an effective dietary intervention compares to control group to help NAFLD individuals to lose weight, lower CAD risk and improving liver status. Specifically, we expected here that MACR regimen, which allowed participants to consume 30% of their energy needs on the fast day, resulted in a mean weight loss between 3-5% from baseline after 8 week of intervention thus it is also expected to decreases in several key biomarkers for CAD risk, such as total cholesterol, LDL cholesterol, triacylglycerols and blood pressure. Liver parameter which included liver enzymes, steatosis and fibrosis would also expect to improve after 8 weeks MACR. Additionally, we expected here that a similar rate of weight loss and adherence rate achieved during the MACR regime when compared with other alternate day calorie restriction regime.

### **Problems Anticipated**

Compliance to dietary modification is one of the problems anticipated while conducting the trial. To overcome this problem, 2 weekly together with designated dietician given to participants in interventional group to monitor the calorie intake as well as education regarding calorie calculations. Besides that, we also will call participants once in a week to ensure the participants comply with dietary modification.

### **Ethical Issues**

This study will be conducted with the highest respect for the subjects according to the study protocol, the ethical principles that have their origin in the Declaration of Helsinki, and the International Conference and Harmonisation (ICH) - Harmonised Tripartite Guideline for Good Clinical Practice (GCP). All researchers of this study will be GCP certified.

The current clinical trial is approved by the Human Research and Ethics Committee of Universiti Sains Malaysia (reference: USM/JEPeM/15040117).

## **1. Subject vulnerability**

1.1 The participants who involved in the study will be provided comprehensive explanation regarding the study procedure, any known adverse reactions, anticipated benefits and potential hazards of the study. If the subject is under my care as a doctor, the patient will be given full freedom to participate or not without affecting her medical condition management and care.

1.2 Participants will not get vulnerable to the study as data obtained from this study does not identify participants individually. Besides that, the data will be independent and will not be used for any achievement assessment and decision related to work

1.3 In addition, participants are given option to terminate their involvement in the study at any time without penalty or loss of benefits if they want to stop. A list of contact number of the investigators will be included in the participants information leaflet and they can directly contact the investigator if they have any queries or opt to cease the study.

## **2. Declaration of absence of conflict of interest**

There is no conflict of interest presence in the study as all the participants are from Gastroenterology Clinic, Hospital USM. The researcher does not hold any supervisory or administrative post over the potential subjects that may influenced the participatory decision making.

## **3. Privacy and confidentiality**

All participants' data including informed consent, medical history, examination will be recorded on the documents prepared for the study. All forms are anonymous and will be entered into SPSS software. Data will be presented as grouped data and will not identify the responders individually.

The medical information will be kept confidential by the study doctor and staff and will not be made publicly available unless disclosure is required by law. Data obtained from this study that does not identify participants individually will be published for knowledge purposes.

## **4. Community sensitivities and benefits**

This study will benefit the participants as well as community. Participants may receive information about their liver status from examination to be done in this study and further treatment will be offer if indicated.

The study allow us to explore the role of MACR in treating NAFLD in addition to exploring feature of NAFLD using new ultrasound techniques. Result and information from the study will provided evidences that modified alternate day calorie restriction (MACR) will be realible alternative ways to improve liver steatosis and fibrosis by weight loss compare to conventional ways.

For community, the study allow us to later educate about NAFLD, including its risk, ultrasound diagnosis and role of modified alternate daily calorie restriction. Furthermore, the findings from study may allow us to apply for larger grants.

## **5. Honorarium and incentives**

Honorarium including transportation cost will be given to the participants during the study.
